Parkinson's disease is a neurodegenerative disease that results in various deficits, including cognitive impairments, for which there is a lack of interventions. Improvisational dance (ID) is spontaneously generated movement, similar to how one moves in everyday life. ID requires the integration of cognitive capacities to execute movements, and thus may strengthen cognitive processes involved in daily life function. ID has been shown to improve motor function in people with PD. The purpose of this study is to understand the effects of ID on cognition and daily function for people with PD. Specifically, it will test the effect of IMPROVment®, a method of ID designed for people with PD, on cognition and daily function. We will conduct a quasi-randomized wait-list controlled trial. Participants will be recruited and screened for eligibility through the St. Louis Chapter American Parkinson's Disease Association. Inclusion criteria includes: 50 years or older, PD diagnosis (mild to moderate), follows simple verbal cues, walks at least 3 meters independently, no contraindications in physical activity, mild cognitive impairment (determined by MOCA score), and no diagnosis of other severe comorbidities. The target sample size is 15-20 participants. Once enrolled, participants will undergo baseline testing (T1). Then participants will be randomly assigned to one of two groups: ID or waitlist control (WC). Participants in the ID group will begin a 12-week intervention where the group will meet once a week for a 1-hour IMPROVment® class. Participants in the WC group will continue with their regular routine for 12 weeks. After 12 weeks, all participants will complete Time 2 testing (T2; primary endpoint). Then WC participants will participate in the same IMPROVment® class for the following 12 weeks followed by Time 3 testing (T3; exploratory endpoint). For primary analysis, assessment scores will be compared across time point (T1, T2) and group (ID, WC) using mixed model ANOVA. Our results will provide further information on the effects of the IMPROVment® method for people with PD.

A2 Primary Hypothesis

The *central hypothesis* is that engagement in an improvisational dance (ID) class will benefit cognition and daily function among people with PD.

A3 Purpose of the Study Protocol

The purpose of this study protocol is to detail the various aspects of this study.

B Background

B1 Prior Literature and Studies

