This is quasi-randomized wait-list controlled trial. Once enrolled, participants will undergo T1 assessments consisting of the primary outcome measures for each aim (described above and attached) and other relevant factors (e.g. demographics, clinical characteristics, motor function). Participants will be randomly assigned (coin flip) to one of two groups: ID or WC group. Although our aim is to randomize participants to the different groups, if someone has a strong preference or inability to participate in one group or the other due to scheduling issues, we will try to accommodate his/her preferences. Each group will have 7-10 participants, a typical size for ID classes. This ensures enough participants to create a cohesive group, but also to provide an appropriate level of safety. The ID group will participate in a 12-week intervention where the group will meet once a week for a 1-hour IMPROVment® class. Participants in the WC group will continue with their regular routine for 12 weeks. After 12 weeks, all participants will complete T2 testing. Then WC participants will participate in the same IMPROVment® method for the following 12 weeks followed by T3 testing.

E2 Subject Selection and Withdrawal

2.a Inclusion Criteria

Inclusion criteria for this study include over 50 years old, PD diagnosis with Hoehn and Yahr stage 1-3 (mild to moderate), independently walks at least 3 meters and ability to comprehend and follow simple verbal cues.

2.a Exclusion Criteria

Exclusion criteria of this study include, a Montreal Cognitive Assessment score less than or equal to 21 (indicating cognitive impairment that may interfere with class participation), diagnosis of other severe comorbidities, and contraindications to physical activity. In addition, participants must attend at least ten of the twelve classes for their data to be included in analysis (they will still be allowed to participate in the classes).

2.b Ethical Considerations

Participants will be given the choice to be involved in the study and may withdraw at any time without penalty.

2.c Subject Recruitment Plans and Consent Process

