Participants may withdraw from this study at any time. To withdraw, participants will tell a member of the study team that he/she is no longer interested in participating in the study. He/she may withdraw completely from the dance classes or continue to dance and just withdraw from testing.

2.g Data Collection and Follow-up for Withdrawn Subjects

Data already collected on participants who withdraw from the study will be securely stored in a RedCap database. With the participants' consent, they may be used for comparison to those who remain in the study or for description of those who withdraw. If a participant would like to withdraw their data, they will be equipped with the procedure to follow on the Human Research Protocol Office website.

E3 Study Drug

NA

F Study Procedures

F1 Screening for Eligibility

Participants will be screened for eligibility using the “Inclusion/Exclusion Criteria Referral Form: IMPROVment® Class Participation” (Appendix 1)

F2 Schedule of Measurements

T1 testing will include the collection of demographics information, National Institute of Health Toolbox Cognitive Battery, the Weekly Calendar Planning Activity, Alternate Uses Task, and the Unified Parkinson's Disease Rating Scale Section 3 Motor exam.

Participants will also be asked to complete the Older Americans Resources and Services scale, Satisfaction with Participation in Discretionary Social Activities scale, the Parkinson Anxiety Scale, the Sleep Disturbance Scale, the Parkinson's Disease Fatigue Scale and the Depression Scale questionnaires. These questionnaires can be completed prior to the first day of intervention via RedCap survey mode or on paper if preferred. In addition, participants will be asked to complete a brief mood questionnaire at the beginning and end of each class. The participant will mark how they are feeling on 4 scales (see Appendix 4).

After the first 12 week period of intervention, both groups will be invited back to complete those same assessments (T2). After the second 12 week period, only the WC group will T3 testing with the same assessments.

F3 Class Structure

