See Adverse Event Reporting Form in Appendix 3. Data on the number and type of adverse events will be collected and reported when study results are disseminated.

4.f Reporting Procedures

See Adverse Event Reporting Form in Appendix 3.

4.g Adverse Event Reporting Period

Adverse events will be reported to the PI immediately (within one day), and the participant will be encouraged to report them to his/her primary care physician or neurologist within the week.

4.h Post-study Adverse Event

NA

G Statistical Plan

G1 Sample Size Determination and Power

Each group will have 7-10 participants, a typical size for ID classes. This ensures enough participants to create a cohesive group, but also to provide an appropriate level of safety. Since this is a pilot study, power analyses were not conducted. Rather, data from this study can be used to power future studies. Although attrition is not anticipated, we aim to recruit 10 participants per group to ensure there are at least 7 participants in the class.

G2 Interim Monitoring and Early Stopping

NA

G3 Analysis Plan

Aim 1: Investigate the effects of IMPROVment® on cognition for people with PD.
Cognition will be assessed at pre (T1) and post (T2) using the NIH (CB), AUT, and WCPA. Scores obtained in these assessments will be compared across time point and group using mixed model ANOVA.

Aim 2: Investigate the effects of IMPROVment® on daily functions for people with PD.
Daily function will be measured at pre (T1) and posttest (T2) using the OARS-EX and SPDSA. Scores will be compared across time point and group using mixed model ANOVA.

G4 Statistical Methods

See above. Analysis will be conducted with IBM SPSS software.

G5 Missing Outcome Data

Participants with missing data will be excluded from analyses involving those data. Since this is a small pilot study, we intend to maximise the use of data we can collect.

G6 Unblinding Procedures

NA (this is not a blinded study)

H Data Handling and Record Keeping

H1 Confidentiality and Security

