J4 Subject Stipends or Payments

Subjects will be given a check for participating in this study.

J5 Study Timetable

Recruitment will occur once the IRB is approved through approximately August 2019, and the study will begin in September 2019. This will ensure ample time for participants to consider participating in the study. Participation in this study is completely voluntary and that will be verbally told to each participant and on the written consent.

Prior to the start of the study, research team members will be trained and checked out on each assessment and the use of RedCap.

Baseline testing will occur in late August 2019, allowing the intervention to begin in September 2019 and run for the following 12 weeks until November 2019. Post testing will occur in that following week. Due to the holiday season and school schedules, the control participants will begin the second wave of intervention in January 2020 until March of 2020.

K Publication Plan

The research team plans to publish findings from this study at its completion.

L Attachments

L1 Tables

Table 1. IMPROVment® Class Components

Components	Class Description
Seated Exercise	Class begins with all participants seated in a chair. Movement cues are given to move different parts of the body in different qualities (i.e. sharp and soft). This part of class serves as a warm up for the body prior to engaging in bigger movements.
Standing Barre Work	Movement progresses from a seated position to standing while still holding onto the chair for extra support. Barre work begins to

	test balance abilities and increase level of movement executed (i.e. balancing on one leg).
Across the Floor	This is the section of class in which ID is incorporated most in several movement activities. These ID tasks are done both individually, in partners, and as a large group. Participants are not limited to staying close to their chairs and move around throughout the space using ID movement (i.e. moving in sync with another person in the room).

Table 2. IMPROVment® Class Themes

Class Themes

Class Themes	Description
Isolation	Movement of a specific body part or parts.
Shape	How the body moves as a whole, as a combination of body parts, or as individual body parts. Shape can also be impacted by other objects in the environment (i.e. chairs, walls, other participants).

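### The 10-of-12 attendance rule decides whose data are analysed, yet by T2 only the ID group has had classes, and no as-assigned analysis is planned

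*Combined protocol and SAP*

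**What the plan says.** The rule is the last item under Exclusion Criteria in E2: "participants must attend at least ten of the twelve classes for their data to be included in analysis". It names neither a group nor an analysis. A parenthesis adds that people who fall short may stay in the classes.

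The study summary makes T2, at 12 weeks, the primary endpoint and T3 exploratory. E1 has controls keep to their usual routine until T2. J5 confirms the order: first-wave classes end in November 2019, T2 testing follows the next week, and "the control participants will begin the second wave of intervention in January 2020 until March of 2020".

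G3 describes the Aim 1 analysis in one sentence: "Scores obtained in these assessments will be compared across time point and group using mixed model ANOVA". Aim 2 is handled the same way. G3 does not mention the attendance rule, an analysis population or a sensitivity analysis.

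Three other places bear on the point:
- G1 makes no power calculation but says that "data from this study can be used to power future studies". Its only allowance for losses is that "we aim to recruit 10 participants per group to ensure there are at least 7 participants in the class".
- G5, on missing outcomes, says "we intend to maximise the use of data we can collect".
- Section 2.g lets data from people who withdraw be used, with consent, to compare them with those who stay or to describe them.

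**The concern.** A baseline eligibility criterion acts on both groups before allocation. This one acts on behaviour after allocation, and at the primary endpoint only one group has had the chance to show that behaviour. If the people who keep coming to class would have changed differently over 12 weeks anyway, removing the others from the ID group alone creates a group difference that the class did not cause.

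The population for the primary comparison is also not fixed. The sentence can be applied to controls in more than one way, so two analysts could follow the plan and analyse different people.

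The data at issue would have been collected: T2 testing is planned for all participants, and low attenders stay in the study. The rule discards observed outcomes in a trial of 15–20 people. Because G1 offers the results for planning later studies, a distorted effect size could carry into their sample sizes.

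**Working it through.** The plan gives no attendance rate, SD, effect size or power, so it has no figure to reproduce. The first step is a reading of the text. The later steps use assumed inputs to show the possible size.

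**1. Three readings of the rule at T2**

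| Reading | Who is filtered | Consequence |
|---|---|---|
| 1 | ID only | Selected attenders against all controls with T2 data |
| 2 | ID, and controls on their January–March 2020 attendance | Control T1–T2 data dropped for behaviour after T2; bias may be near zero if the filter acts alike in both groups, but data are lost |
| 3 | Everyone, on classes attended by T2 | Every control has attended none, so no control remains |

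**2. How many would qualify**

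Assume each class is attended independently with probability q. The fraction kept is k = P(Bin(12, q) ≥ 10). For q = 0.85, k = 0.292 + 0.301 + 0.142 = 0.736 (the terms for 10, 11 and 12 classes, summed before rounding). With 10 per group:

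| q | k | ID analysed of 10 | P(at least 7 of 10 kept) |
|---|---|---|---|
| 0.95 | 0.980 | 9.8 | about 1.00 |
| 0.90 | 0.889 | 8.9 | 0.98 |
| 0.85 | 0.736 | 7.4 | 0.74 |
| 0.80 | 0.558 | 5.6 | 0.28 |

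Reading 1 sets these against 10 controls. Under reading 2, if controls attend at the same rate, the total analysed is 19.6, 17.8, 14.7 or 11.2 of 20. G1's margin from 10 down to 7 concerns numbers in the class, not numbers left after this rule.

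**3. Bias under reading 1 with no true effect**

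Let r be the correlation between a person's tendency to attend and their T1–T2 change, and let the lowest fraction p = 1 − k be excluded. The ID mean shifts by r·φ(z_p)/(1 − p), in SDs of change, where z_p is the standard normal p-quantile. The standard error of the group difference is √(1/(10k) + 1/10).

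For q = 0.85: p = 0.264, z_p = −0.631 and φ = 0.327, so the multiplier is 0.327/0.736 = 0.444. At r = 0.3 the shift is 0.133. The standard error is √(1/7.36 + 0.1) = 0.486.

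| q | r = 0 | r = 0.3 | r = 0.5 | SE |
|---|---|---|---|---|
| 0.95 | 0 | 0.015 | 0.024 | 0.449 |
| 0.90 | 0 | 0.064 | 0.106 | 0.461 |
| 0.85 | 0 | 0.133 | 0.222 | 0.486 |
| 0.80 | 0 | 0.212 | 0.353 | 0.528 |

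A negative r reverses the sign. Every shift is below one standard error.

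**4. Check with a single model**

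Step 3 takes k from independent attendance but the bias from truncating a latent trait. As a check, one normal trait was made to drive both attendance (logit slope 1.0, mean attendance 95/90/85/80%) and change (correlation r), with 2,000,000 draws. The fraction kept was 0.951/0.845/0.725/0.609. The shift was 0 at r = 0, 0.025/0.068/0.111/0.154 at r = 0.3, and 0.042/0.112/0.186/0.257 at r = 0.5. The order of magnitude is the same.

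**5. Knock-on for a later trial**

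Assume a true effect of 0.5 SD, two-sided 5% and 80% power, with n per group = 2(1.960 + 0.842)²/d².
- d = 0.5: n = 62.8, so 63.
- d = 0.633 (bias +0.133): n = 39.2, so 40. True power is then Φ(0.5·√20 − 1.960) = 0.61.
- d = 0.367 (bias −0.133): n = 116.5, so 117.

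These are normal-approximation values. The t-test values are 64, 41 and 118, with power 0.60 at 40 per group.

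**The case against.** The strongest reply is that the three readings are not equally plausible. Reading 3 deletes one arm of a comparison that the plan defines as ID against WC. Nothing in the documents positively supports reading 2. The parenthesis about staying in the classes suits people taking classes at the time, which before T2 means ID only. This is fair: reading 1 is the natural one. It does not rescue the rule, because reading 1 is the one that filters a single arm.

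Second, E2 does set a numeric threshold in advance, and the central hypothesis in A2 concerns engagement in the class. Wanting the effect in people who attended is a legitimate question, and part of any link between attendance and change in the ID group may be a real dose effect. That stands as a reason to keep a completer analysis. It does not justify making it the only analysis, since the matching controls (those who would have attended) are not identified at T2.

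Third, the trial is a small, unblinded pilot, allocation partly follows preference (E1, 2.d), and every bias figure rests on assumptions and is below one standard error. All true. An as-assigned analysis will not remove selection at allocation, and restricting it to people with T2 data still leaves attrition. The attendance filter is nevertheless a further source of selection, and an avoidable one.

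Fourth, G5 concerns missing scores, not entry to the analysis. The tension with its stated wish to use the data is therefore one of spirit and carries little weight here.

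**Conclusion.** The concern holds and should be fixed before analysis. What follows from the text alone is certain: entry to the analysis depends on attendance after allocation, controls have attended nothing by the primary endpoint, the plan does not say how the rule treats them, and no section provides an as-assigned comparison.

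The size of any bias is unknown. It depends on attendance and on its relation to change, neither of which the documents give. Across the assumed range (attendance 95% to 80%, r from 0 to 0.5) it runs from zero to about 0.35 SD of change, with the opposite sign if r is negative. It would not stand out against the trial's own imprecision, but it could move a later trial's sample size substantially in either direction. The finding does not depend on these assumed values.

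**What to change.** In E2, remove the attendance sentence as a condition for the primary analysis. In G3, add wording such as:

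> The primary T1–T2 analysis includes every participant with T2 data, in the group assigned, regardless of classes attended. A secondary completer analysis limits the ID group to those who attended at least 10 of 12 classes and is labelled as such. The 10-of-12 rule is applied to WC only in the exploratory T2–T3 look. Classes attended are reported for each group.

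Two clarifications would help. For people placed by preference or scheduling, state that the group assigned means the group in which they were placed. In 2.f, state that people who leave the classes are still invited to T2 testing, in line with E1 and F2, which already plan T2 for both groups. G3 does not yet describe any T3 analysis, so the T2–T3 look needs a line of its own.

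The cost is protocol and SAP wording only, with no extra visits. The downside is that the primary estimate becomes the effect of being offered the class. It may be somewhat smaller than the effect in high attenders, which the secondary analysis still reports.

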Participants will be recruited and screened for eligibility through the St. Louis Chapter American Parkinson's Disease Association (APDA). Approximately 15-20 participants diagnosed with PD will be recruited for this study. Consent will be obtained from each participant by select members of the research team. Each participant will be walked through the informed consent document in detail and allowed to ask questions with no cohesion. Participants will be re-assented to additional research processes after 9.24.2019 upon IRB reapproval.

2.d Randomization Method and Blinding

After consent is given and T1 testing is completed, participants will be randomly assigned (coin flip) to either participate immediately (i.e., starting the next week) in 12-weeks of IMPROVment (ID group) or to continue with regular routine for 12 weeks before starting IMPROVment (WC group). Once we reach 10 participants in a group, remaining participants will be assigned to the other group. In addition, if the participant would like to be a part of this study, but can only participate in one group or the other, we will try to accommodate his/her needs.

2.e Risks and Benefits

Risks:

Participation in this study could result in the following risks. In addition to these, there may be other unknown risks, or risks that we did not anticipate, associated with being in this study.

One risk of participating in this study is that confidential information about participants may be accidentally disclosed. We will use our best efforts to keep the information about participants secure.

Another risk of participating in this study is an increased risk for falls. Although we do not expect the participants to fall during the intervention, precautionary measures are in place to decrease this risk (i.e. certified therapist present at all times, OT students monitoring the participants, movement modifications sitting in a chair).

Benefits:

Participants will not directly benefit from being in this study. Participants may indirectly benefit from participating in this study with the increased social participation and entertaining nature of the study program.

However, we hope that, in the future, other people might benefit from this study because it will help to provide information on how people with PD can best learn and remember in their daily lives.

2.f When and How to Withdraw Subjects

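### The T1 scores are available before assignment but are used neither as a covariate in G3 nor to balance the groups in 2.d, so a valid comparison gives up some precision

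*Combined protocol and SAP*

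**What the plan says.** - **Assignment (2.d Randomization Method and Blinding):** "After consent is given and T1 testing is completed, participants will be randomly assigned (coin flip"), to immediate classes or to the waiting list. No stratification, pairing or minimisation is described. A running cap applies: "Once we reach 10 participants in a group, remaining participants will be assigned to the other group". The cap implies one flip per person.
- **Exceptions (2.d):** for someone who "can only participate in one group or the other, we will try to accommodate his/her needs". E1 has a similar provision. The number of such placements is not stated.
- **Timetable (J5):** "Baseline testing will occur in late August 2019, allowing the intervention to begin in September 2019". Everyone is therefore tested in one batch before a single start.
- **Size (2.c and G1):** "Approximately 15-20 participants diagnosed with PD will be recruited for this study"; "Each group will have 7-10 participants, a typical size for ID classes".
- **Analysis (G3, Aim 1):** "Scores obtained in these assessments will be compared across time point and group using mixed model ANOVA". Aim 2 uses the same method. No covariate is named, and none of the three Aim 1 instruments is designated as leading.
- **Power (G1):** "Since this is a pilot study, power analyses were not conducted".

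**The concern.** In groups of 7-10, separate coin flips can easily leave the two groups apart at T1. With two time points, the time-by-group test is a comparison of mean change. A T1 gap enters that comparison through regression to the mean: the group that starts higher tends to appear to gain less. This is part of the random error of the estimate, and it could be reduced with data already collected. G1 says that the results may be used to power later studies, so less noisy estimates would serve the plan's own purpose. The issue here is chance imbalance and precision. Selection through preference placement is a separate matter.

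**Working it through.** **Inputs.** From the documents: N = 15-20; cap of 10 per group; stated group size 7-10; T1 before assignment; time-by-group ANOVA without a covariate. Assumed, because the documents give no values: normal scores with equal SD at T1 and T2; T1-T2 correlation r = 0.6-0.8; no dropout; everyone flipped unless stated; for power, a true effect of 0.8 SD. The plan has no power or imbalance figure to reproduce.

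**1. Chance of a T1 gap above 0.5 SD with separate flips.** For group sizes n1 and n2,

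P = 2 × [1 − Φ(0.5 / √(1/n1 + 1/n2))].

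- 8/8: √(1/8 + 1/8) = 0.500, so P = 2 × [1 − Φ(1.00)] = 0.317.
- 10/10: √(1/10 + 1/10) = 0.447, so P = 2 × [1 − Φ(1.12)] = 0.264.

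Averaged over the group sizes that capped flips produce:

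| N | 15 | 16 | 17 | 18 | 19 | 20 |
|---|---|---|---|---|---|---|
| P | 0.345 | 0.326 | 0.308 | 0.291 | 0.277 | 0.264 |

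This is about 3 in 10 for any one score.

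**2. What a gap does to the planned contrast.** With no class effect and a T1 gap g, the expected T2 gap is r × g, so the difference in change is −(1 − r) × g. For g = 0.5 SD the size is 0.5 × 0.4 = 0.20 SD at r = 0.6 and 0.5 × 0.2 = 0.10 SD at r = 0.8. The standard error of the contrast is √(2(1 − r) × 2/n). With n = 8 it is √(0.8 × 0.25) = 0.447 at r = 0.6 and √(0.4 × 0.25) = 0.316 at r = 0.8. With n = 10 it is 0.400 and 0.283. The shift is thus about a third to a half of one standard error.

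**3. Adding T1 as a covariate.** The variance becomes (1 − r²) × 2/n. Its ratio to the change-score variance is (1 − r²) / [2(1 − r)] = (1 + r)/2, which is 0.80 at r = 0.6 and 0.90 at r = 0.8, before the small cost of estimating the slope. Simulated power under separate flips, 0.8 SD effect, r = 0.6:

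| | Planned ANOVA | With T1 covariate |
|---|---|---|
| N = 16 | 0.375 | 0.423 |
| N = 20 | about 0.48 | about 0.54 |

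At r = 0.8 the power gain is small.

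**4. One flip per T1-matched pair (simulated).**

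- *On the paired score:* P(gap > 0.5 SD) is about 0.001 at N = 16 and 0.0001 or less at N = 18-20. At N = 15 it is up to 0.04, depending on which person is left unpaired.
- *On another score,* by its correlation with the paired one:

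| Correlation | 0.9 | 0.7 | 0.5 | 0 |
|---|---|---|---|---|
| N = 16 | 0.05 | 0.18 | 0.26 | 0.32 |
| N = 20 | 0.02 | 0.13 | 0.20 | 0.27 |

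- *Pairing on the mean of three cognitive scores* with mutual correlation 0.7 down to 0.2: each score has 0.05-0.19 at N = 16 and 0.02-0.14 at N = 20.
- *With preference placements* unrelated to score, N = 18, on the paired score: 0.01 with 2 people placed, 0.05 with 4, 0.14 with 8.
- *Effect on the planned ANOVA without a covariate* (N = 16, r = 0.6): the true spread of the estimate falls from 0.456 to 0.404, but the mean reported standard error barely moves (0.449 to 0.443). Power is 0.375 against 0.374, and type I error drops from about 0.05 to about 0.03.
- *On top of the covariate:* roughly 0-0.04 more power.

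**5. Group size.** The cap enforces the upper limit of 10 but not the lower limit of 7. At N = 15 only a 7/8 split meets it: 2 × 6,435 / 32,768 = 0.393, so a group falls below 7 with probability 0.607. At N = 16 the 8/8 and 7/9 splits meet it: (12,870 + 2 × 11,440) / 65,536 = 0.546, leaving 0.454. At N = 17-20 the cap itself guarantees 7. Pairing everyone gives 7/8 or 8/8.

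**The case against.** The strongest reply is that nothing here is invalid. A fair coin flip makes chance imbalance part of ordinary sampling error, and the ANOVA's error term already covers it: simulated type I error is about 0.05. T1 is in the model as a repeated measure, so a raw gap does not carry over in full. This is a declared pilot without a power target, and simple randomisation is a legitimate choice. All of that stands. A reader might infer from the 3-in-10 figure that the planned test is biased or its error rate wrong; the plan and the calculation do not support that.

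A reader might also infer that pairing alone would sharpen the planned analysis. It would not: the ANOVA's standard error does not register the pairing, so the test becomes conservative and power does not improve. The dependable gain comes from the covariate.

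Practical limits stand too. G3 names no lead score to pair on. Under F2 the OARS-Ex and SPDSA questionnaires may arrive after assignment, up to the first class. The attendance rule in 2.a (ten of twelve classes) and the missing-data rule in G5 can break pairs. What remains is that the covariate costs nothing to collect, and pairing is cheap where the timetable allows it.

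**Conclusion.** The concern holds as a modest loss of precision. The coin flip and the ANOVA give a valid test, but they leave T1 information unused: a gap above 0.5 SD on a given score has probability 0.26-0.35, and such a gap is worth 0.10-0.20 SD in the change contrast. Adjusting for T1 recovers most of what can be recovered, about 0.05-0.06 in power at r = 0.6 and little at r = 0.8. Pairing is a secondary improvement.

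It would be tempting to say that pairing nearly removes baseline imbalance in this trial. That is true only for the score used to form the pairs. With several instruments and no lead score, a measure correlated 0.5 with the paired one still shows a gap above 0.5 SD with probability 0.20-0.26. Pairing also does nothing about selection through preference placement.

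The sizes rest on assumed normality, correlations and effect size, and on few preference placements or exclusions. The point is an optional improvement, not a defect that undermines the trial.

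**What to change.** 1. **G3, first priority.** For each outcome, compare T2 between groups with that outcome's T1 score as covariate. This costs one sentence and one degree of freedom and needs no new data. It can be adopted at any time before T2 data are analysed.
2. **2.d, optional, before any assignment.** Name one T1 cognitive score or composite in advance. After the last T1 visit, rank the participants who can attend either group on it, join neighbours into pairs, and flip once per pair; an odd person gets a single flip. Keep the pairing score in the model, and keep the remaining member if a partner is lost. Do not adopt this step without the covariate.

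The second step costs one paragraph and no extra visit. Its burdens are that T1 must be scored for everyone before the draw, while 2.d has classes starting the following week, and that a pairing score must be chosen. Its benefit shrinks as preference placements and attendance exclusions increase. Report the number placed by preference separately, since neither step corrects for that selection.
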